6.2.2 Randomization and Baseline

Randomization (Wk -4 to 0)

Once the PI and Co-Investigators have determined that a participant has satisfactorily met all inclusion/exclusion criteria, the participant will be randomized by the study coordinator (this could be done at any time from week -4 to week 0 as long as consenting and screening come first). The date of randomization will be recorded on the Enrollment Log.

The maximum allowable time between enrollment and randomization is 4 weeks. If screening and determination of eligibility goes beyond this allowable window, the participant will need to be re-screened before randomization.

Baseline Assessments (Week 0; See Figure 4)

Baseline assessment occurs within 4 weeks from the time of enrollment (regardless of when baseline assessment occurs relative to screening, Baseline Assessment is identified as Week 0).

For participants who have successfully been screened for eligibility and are randomized into the study, baseline assessments are performed to measure the study outcomes. They also ensure that the groups are balanced with respect to baseline characteristics.

Baseline evaluations for this study include:

Assessments (Domain Assessed)	Assessment Window	Special Instructions
----------------------------------	----------------------	----------------------

Health Questionnaire / Addendum (previous pain treatments) (comorbid pain/medical conditions)	≤ 2 weeks before treatment start	Balance Sample Past medical history will not change, so this measure is only given once
Concomitant Medications and Medication Quantification Scale- III (medications that may impact pain) (medications that may impact mood)		Control: Other Medications Medications may change, so this will be assessed at all assessment visits; self-report and CPRS review
Timeline Follow-back Interview (opioid & other pain medication use)		Endpoint: Hypothesis 3 Assessed at all assessment visits
Oswestry Disability Index (self-report disability)		Endpoint: Hypothesis 1 Veterans cannot participate with moderate to severe TBI- related cognitive impairment
PHQ-9 (depression symptoms)		Endpoint: Hypothesis 2 Assessed at all assessment intervals
PTSD Checklist – 5 (PTSD symptoms)		Endpoint: Hypothesis 2 Assessed at all assessment intervals
Depressive Symptom Inventory- Suicidality Subscale (DSI-SS) (suicidal ideation or intent)		Risk Surveillance Suicide risk is not a research endpoint, but if suicide risk is present at a previous assessment (e.g., any positive response for BSSI screening items) then BSSI will be repeated at the next assessment interval (unless participant is disenrolled for a VA mental health treatment referral)
Functional Capacity Evaluation (objective disability)		Endpoint: Hypothesis 2 Assess at all assessment intervals
Pain Catastrophizing Scale (pain-related cognitions)		Endpoint: Hypothesis 2 Variable: Exploratory
Interpersonal Needs Questionnaire (Burdensomeness)		Endpoint: Hypothesis 2 Variable: Exploratory
Fear Avoidance Beliefs Questionnaire		Endpoint: Secondary Objectives Variable: Exploratory
Chronic Pain Acceptance Questionnaire	Endpoint: Secondary Objectives	

		Variable: Exploratory
Multidimensional Pain Inventory		Endpoint: Secondary Objectives Variable: Exploratory
Generalized Anxiety Disorder- 7 item		Endpoint: Hypothesis 2 Assess at all assessment intervals
Current Opioid Misuse Measure		Endpoint: Hypothesis 4 Assess at all assessment intervals
Actiwatch		Endpoint: Hypothesis 2 Assess at all assessment intervals
MEMS eCap		Endpoint: Hypothesis 4 Assess at all assessment intervals
Treatment Helpfulness Questionnaire		Endpoint: Secondary Objectives Variable: Exploratory Only given post-treatment
Subjective Opiate Withdrawal Scale		Endpoint: Hypothesis 4 Assess post-treatment and at follow-ups
Pain Diary		Endpoint: Hypothesis 2 Assess at all assessment intervals
Phone Contact (Adherence/AE/MEMS/Actiwatch)		Treatment Adherence Occurs at all assessment intervals
Quick Drinking Scale (QDS)		Common Data Element with STRONG STAR Studies
Fagerstrom Test for Nicotine Dependence (FTND)		Common Data Element with STRONG STAR Studies
Fagerstrom Test for Nicotine Dependence – Smokeless Tobacco (FTNB-ST)		Common Data Element with STRONG STAR Studies

Randomization

As noted above, participants will be randomly assigned to the FORT-A or PRC on a 1:1 allocation ratio using a randomly selected block size with randomly permuted assignments within blocks.

In the original FORT study we found that the ideal treatment group size for each iteration of the program was 5 participants (though successful groups were able to run with as few of 3 members and as many as 7). Thus, we will attempt to fill treatment

cohorts for FORT-A and PRC with between 3 to 7 participants (as described in Efrid, 2011). The coordinator and co-coordinator will be blinded to all randomization assignments but will initiate a treatment cohort when a sufficient number of participants have been assigned.

There is a four-week window between enrollment and baseline assessment (Week -4 to Week 0, as shown in 6.1). Study intervention must begin within 2 weeks after baseline to ensure that baseline assessment data adequately represent *current* functioning at the time of treatment, especially functional capacity evaluation [FCE] data that are used to guide the physical therapy portion of the interdisciplinary intervention. Test-retest reliability of FCE has been confirmed over a period of two weeks (Brouwer et al., 2003), with only slight fluctuations in more frequent testing resulting in a slight increase in lifting capacity if repeated across two days, likely due to practice effects (Reneman et al., 2002). Thus, intervention will generally begin within 5 weeks of enrollment.

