3. STUDY DESIGN

To address the primary and secondary hypotheses, this research study was designed as a randomized clinical trial comparing the manualized FORT-A treatment to treatment as usual for polytraumatic chronic musculoskeletal pain in the STVHCS Polytrauma Rehabilitation Center. Eligible OEF/OIF/OND Veterans will be randomized to either arm in 1:1 random permuted block randomization with no stratification. Because the FORT-A is a group intervention, it is vital that we randomize into meaningful blocks of at least three Veterans and no more than seven. Three is chosen as the lower block boundary because the PI had success in the original FORT trial with FORT groups of three active duty service members. Seven Veterans will be the upper boundary because FORT groups of more than seven military members were difficult to manage. In block randomization with static boundaries, study staff overseeing randomization will lose blinding if they are aware of how many participants have already been randomized into each block. For example, if block boundaries are always 5 participants and the treatment as usual condition has 5 participants while the active treatment has 4, then the staff randomizing the 10th participant will know with certainty that this participant will be in the active treatment group. To protect blinding, we have chosen to implement a variable boundary randomization for which the study staff randomizing patients will be blind to the boundaries and the resulting condition of the participant (see Sanghaei, 2011). The PI, Independent Evaluators, and Biostatistician will be blind to the condition of all participants until data lock. A research assistant overseeing randomization will also be blinded by randomizing unique patient identifiers into variable permuted blocks (through the STRONG STAR Data Core) by unique study identifier (e.g., first participant identified as #0001). All assessments given by Independent Evaluators will be labeled with just the unique identifier. Only the study coordinator (and co-coordinator) will be able to link unique identifiers to individual participants.

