4.3 Study Enrollment Procedures

- Potential participants may be directly referred to the study by their VA provider or may directly contact the study coordinator on their own in response to flyers/pamphlets distributed at VA clinics

- Consistent with current STRONG STAR practices, we will maintain an Enrollment Log describing the timeline of screening and consent as well as the disposition and reason for enrollment/disqualification (see **Appendix A3**).
- Consent for participation in this research will take place in the South Texas Veterans Health Care System (STVHCS) PRC or on the STVHCS Barter Research Unit (BRU). Potential participants who are referred by a provider or who self-refer in response to a flyer will call the study coordinator and arrange a time to meet and discuss the study. Those who sign a **Consent to Contact** form after meeting with their physician at the STVHCS (**Appendix A1**), will receive a phone call from the study Coordinator. Participants will be asked to meet individually in a private room at the PRC/BRU with the Coordinator where they will be told about the study and will have an opportunity to ask any questions they may have of the Coordinator. Potential participants will be given a copy of the study informed consent document (ICD, **Appendix A2**) and will be allowed to take it home with them if they wish to take time to read it. Upon reading the document, the potential participants will have an opportunity to ask questions about the study and may meet with a study investigator to address their questions. Consistent with STRONG STAR procedures, the Coordinator will have a checklist of questions about the ICD that they will ask the potential participants to ensure that they understand. Once understanding is confirmed, the participants will sign the ICD and be enrolled into the study and recorded on the NCCIH Enrollment Form (**Appendix A3**). A unique identifier will be assigned to the participant using a code developed in accordance with the STRONG STAR Unique Identifier SOP (**Appendix A4**).

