- Participants will be randomly assigned into one of the two study arms (FORT-A, Treatment as Usual) on a 1:1 ratio. Participants will be randomized using variable sized blocks of an even number to maintain a balance within blocks. One weakness of block randomization is that blinded study staff who are aware of established block sizes will be able to predict, with increasing certainty, how a participant will be randomized as blocks fill. This does pose a threat to blinding and creates an opportunity for non-random assignment (e.g., cherry picking a participant who may be a particularly good responder to be “randomized” into the experimental condition). To maintain a blinded assignment schedule, we have chosen to work with the STRONG STAR Biostatistics and Data Core to execute the randomization schedule, hold the blinded assignments, and administer them to the study Coordinator sequentially during enrollment (i.e., the Coordinator and study team will always remain blinded to the next assignment)

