6.2.3 Blinding

Blinding in an interdisciplinary behavioral intervention is extraordinarily difficult since the intervention requires face-to-face contact and continuity of an interdisciplinary approach requires different interventionists to be able to talk to one another about patient progress. This is particularly true in trials of openly symptomatic conditions (like chronic pain; see Friedberg, Lipsitz, & Natarajan, 2010). There is no placebo control for an intervention like this (nor would the VHA allow one), so blinding is best accomplished through careful consideration of “need to know” privileging. Figure 2 provides a visual representation of who needs blinding and who is allowed to maintain awareness of patient identity. The entire study staff will be thoroughly briefed on the importance of maintaining blinding and the study coordinator will attend all study meetings and help ensure that blinding is maintained when blinded and unblinded personnel discuss the study participants. We have chosen to use a multi-level blinding scheme (as described by Friedberg et al.) in which study personnel will be blinded to randomized treatment **condition**, assessment **outcomes**, or **both** (as shown in Figure 2).

Study interventionists and their supervisors (for group psychosocial treatment; individual psychotherapy; biofeedback, and physical therapy) cannot be blinded to **condition** because they will be aware of the treatment condition of the patients they treat. Research Assistants (RA’s), blinded to participant identity, will listen to audio recordings of treatment sessions and will rate adherence to the treatment manual using a standardized checklist (see Section 10.3 Quality Assurance) for more information about this. The Research Coordinator and Co-Coordinator will be aware of participant condition (because they are responsible for randomizing and because they need to assist with adverse events monitoring and administrative oversight of treatment and assessment procedures), but they will be blinded to **outcomes**. The Coordinator and Co-Coordinator will not be directly involved in treatment or assessment and will be asked to only refer to participants by their unique identifiers when discussing participants with RA’s, the PI, or IE’s. Independent Evaluators will

become aware of outcomes during the course of their assessments, but will be blind to **condition** of the participants they assess.

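### The safeguards against predicting assignments contradict each other, and no rule fixes the order of entry, so the cherry-picking that the protocol warns of is not ruled out

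*Combined protocol and SAP*

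**What the plan says.** **Who randomises and when.** Section 6.2.2 has the study coordinator randomise each participant found eligible and says of the timing that "this could be done at any time from week -4 to week 0 as long as consenting and screening come first". It caps the interval from enrollment to randomisation at four weeks. Section 6.2.1 has eligibility settled at a weekly meeting and participants randomised once confirmed eligible, with no deadline and no order. Section 3, by contrast, has a blinded research assistant oversee randomisation.

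**Who meets candidates.** Under Section 4.3 candidates "meet individually in a private room at the PRC/BRU with the Coordinator where they will be told about the study", and "the Coordinator will have a checklist of questions about the ICD that they will ask the potential participants to ensure that they understand".

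**Who knows past assignments.** Section 6.2.3 says the Coordinator and Co-Coordinator "will be aware of participant condition (because they are responsible for randomizing". Section 9.2 (Treatment Assignment Procedures) says the Coordinator is blind to no part of the study. Section 6.2.2 says both coordinators are blinded to all assignments, yet the same sentence says that they "will initiate a treatment cohort when a sufficient number of participants have been assigned".

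**Block sizes.** Section 3: "it is vital that we randomize into meaningful blocks of at least three Veterans and no more than seven". Section 4.3: "Participants will be randomized using variable sized blocks of an even number to maintain a balance within blocks". Section 6.2.2 gives 3 to 7 as the size of a treatment cohort.

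**Safeguards claimed.** Section 3 says randomising staff will not know the block boundaries. Section 4.3 has the Data Core hold the list and release assignments one at a time, so that the next one stays unknown.

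**The concern.** Releasing assignments one at a time hides the list. It does not stop someone from inferring the next assignment from those already made. With permuted blocks, preventing that inference from mattering takes at least one of three things: the history is hidden from whoever controls entry, the block sizes are unknown to that person, or the order of entry is fixed. The current text secures none of them clearly. The history is both open and closed to the Coordinator, depending on the section. The block limits are printed in the protocol. The order of entry is not addressed.

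The stakes are higher than in a masked trial. Section 9.2 accepts that participants and providers cannot be masked, and the primary outcome is self-reported disability. If Veterans with a better outlook tended to enter when FORT-A was the likelier next arm, the arms would differ in prognosis from the start.

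**Working it through.** **1. The protocol's own example.** Section 3 takes a fixed boundary of 5 per arm with a 5 to 4 split and says the tenth assignment is known. In a block of size b, P(next is active) = (b/2 − active so far) / (b − assigned so far) = (5 − 4)/(10 − 9) = 1. The example is right. It concerns fixed blocks, so the question is how much predictability remains when sizes vary.

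**2. Which sizes are possible.** The even numbers from 3 to 7 are 4 and 6. If 3 to 7 means the number per arm, as the match with the cohort limits suggests, total sizes are 6, 8, 10, 12 or 14. The text does not say which reading applies, so both are shown.

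**3. Predictability.** Inputs: 130 participants, 1:1, no stratification (Section 3). Assumptions: the observer knows every past assignment and the set of possible sizes but not the size drawn, and sizes are equally likely. Sequences were simulated. At each entry the observer's probabilities for block size and position were updated by Bayes' rule and the likelier arm was guessed.

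| Block sizes | Correct guesses | Next arm predictable at 2/3 or more | at 0.75 or more | Certain |
|---|---|---|---|---|
| 4, 6 | 69% | 58% | 49% | 5.4% |
| 6 to 14, even | 65% | 52% | 19% | 0.6% |

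Chance is 50%. For comparison, fixed blocks of 4, 6 and 10 give 1/3, 1/4 and 1/6 certain assignments, from 1/(b/2 + 1). Varying the size therefore removes most of the certainty but leaves much of the average predictability.

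**4. What it could do to the ODI (illustration only).** Suppose every choice of who goes next shifts that person's expected 12-month ODI by δ, down when FORT-A is guessed and up when usual care is guessed. With a correct-guess rate g, each arm mean moves by δ(2g − 1) in opposite directions, so the bias is 2δ(2g − 1). With δ = 1 point (assumed; no source in the protocol):

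- blocks of 4 or 6: 2 × 1 × (2 × 0.691 − 1) = 0.76 points
- blocks of 6 to 14: 2 × 1 × (2 × 0.649 − 1) = 0.60 points

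Against the 3.3-point target difference in Section 9.2 these are 0.76/3.3 = 23% and 0.60/3.3 = 18%. The formula applies the shift at all 130 entries, including those with only one person available, so for a given δ it is an upper figure.

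**5. How often there is a choice.** Section 3 gives a 5-year trial. If accrual takes about 4 years (assumed), 130/(4 × 52) = 0.625 people become eligible per weekly meeting. With Poisson arrivals and prompt randomisation, P(two or more in a week) = 1 − e^(−0.625) × (1 + 0.625) = 13%. A choice of order would arise in about one week in eight, and more often only if eligible people were held back.

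**The case against.** A reader might infer something stronger: that the Coordinator knows every assignment, chooses when each person enters, and so produces a bias of about a fifth of the target that no analysis can undo. The documents do not support that.

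- **Knowledge of assignments is contradictory, not established.** Sections 6.2.3 and 9.2 say the Coordinator knows. Section 6.2.2 says the opposite, and Section 3 names a blinded research assistant.
- **Control of timing is not assigned to anyone.** Section 6.2.2 says when randomisation may happen, not who decides. Section 6.2.1 points to randomisation once eligibility is confirmed, and the PI and Co-Investigators confirm it. The four weeks also have to hold screening, the eligibility meeting and the baseline visit, so the real slack is shorter.
- **Cohort filling does not create a queue of unassigned people.** Cohorts start after enough people have been assigned, so that wait follows randomisation. The weekly meeting is the only place where the text suggests that several people may be cleared together.
- **The true block sizes may be unknown to the Coordinator.** The Data Core holds the list, and the printed limits are ambiguous.
- **The bias figure needs deliberate ordering**, and the primary ANCOVA in Section 9.6 adjusts for baseline ODI.

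Most of this stands. It limits the claim to a gap and a set of contradictions and makes the bias figure hypothetical. Two things survive it. Baseline adjustment removes only the part of any selection carried by baseline ODI, not motivation or other prognostic features. And a safeguard that depends on which section is followed cannot be relied on, least of all against a threat that Section 4.3 itself describes.

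**Conclusion.** The concern holds as a defect in the written safeguards. It is not evidence that assignments will be predicted or that bias will occur. Sections 3, 4.3, 6.2.2, 6.2.3 and 9.2 disagree on who randomises and who knows past assignments. The block limits are printed although they are meant to be hidden, conflict with the even-size rule, and coincide with the cohort limits. No section fixes the order of entry among people cleared together.

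Under full knowledge of the history and the possible sizes, correct guesses reach about 69% or 65% rather than 50%, with about 5% or 0.6% of assignments certain. These figures assume equally likely sizes. The 0.6 to 0.8 point ODI bias is an illustration that rests on an assumed 1-point shift at every entry and on intent. It should not be read as an estimate. The point merits a change because the remedy is cheap, not because a large bias is shown.

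**What to change.** 1. In Section 6.2.2, have the Data Core randomise in strict order of eligibility sign-off, either promptly after each sign-off or as one batch per weekly meeting submitted in a single transaction. Nobody then chooses who is next after seeing an earlier result.
2. Reconcile Sections 3, 4.3, 6.2.2, 6.2.3 and 9.2 so that they name one role that requests randomisation and state who knows past assignments.
3. Correct the block-size text so that it agrees with the even-size rule, and separate it from the 3 to 7 cohort limits. Move the actual sizes to a document restricted to the Data Core.

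This is procedural wording. It needs no extra staff, since the Data Core already holds the list. The cost is less freedom in when a participant is randomised. With the order fixed, a correct guess can no longer be used to decide who enters next, and the bias by this route is zero.
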